6.2 Secondary Endpoints

1. Post-ablation inducibility (if performed at procedure conclusion)
2. Time to ventricular arrhythmia termination (if ablation is performed during ventricular arrhythmias).
3. Total duration of intramural needle ablation
4. All-cause mortality

* - For patients who have been re-enrolled after the six-month follow-up is complete, primary and secondary endpoints will be re-assessed at six months post-second procedure.

7 STUDY SUBJECTS

7.1 INCLUSION CRITERIA

1. The study will include patients with any of the following criteria: a) monomorphic ventricular tachycardia (VT); b) frequent ventricular arrhythmia (defined as unifocal PVCs, couplets, non-sustained VT) with a PVC burden $\geq 13\%$, or is causing a decline in left ventricular (LV) ejection fraction to $\leq 40\%$; or c) previous failed ablation for one or more of the criteria above.
2. ≥ 16 years of age.
3. Left ventricular (LV) ejection fraction $> 10\%$ as estimated by echocardiography, CT/MRI, contrast ventriculography, or radionuclide imaging within the past 90 days.
4. Clinical indication for catheter ablation of VT
5. Intramural ventricular arrhythmias not terminable with standard ablation once enrolled in the Intramural Needle Ablation study or previous failed ablation within 6 months prior to enrollment.
6. Ability to understand the requirements of the study and sign the informed consent form. For potential patients aged < 18 , parental consent will be required along with subject assent.
7. Able and willing to comply with all pre-, post-, and follow-up testing and requirements.
8. Projected lifespan greater than 1 year.

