Patients will be excluded from the trial if: 1) history of MI or CABG within 6 weeks; 2) Class IV HF; 3) Idiopathic ventricular arrhythmias defined as VT or PVCs that occur without evidence of structural heart disease and that are not causing significant depression of LV function; 4) pregnant; 5) Definite protruding left ventricular thrombus on pre-ablation echocardiography or other imaging modalities; 6) contraindication to heparin; 7) allergy to radiographic contrast dye; 8) unstable angina that is not due to frequent or incessant VT; 9) acute non-cardiovascular illness or systemic infection; 10) thrombocytopenia (platelet count $< 50,000 \text{ mm}^3$) or coagulopathy; 11) cardiogenic shock unless it is due to incessant VT; 12) unable to sign consent; 13) projected lifespan of < 1 year. Patients are considered enrolled once consented. Patients who do not undergo ablation of ventricular arrhythmias within 90 days of enrolling will be considered to be screen failures. Patients successfully terminated with standard ablation once enrolled will be followed in a registry for 6 months, (adhering to the same post-procedure schedule as the patients that underwent intramural needle ablation). Two hundred subjects are

	expected to be enrolled in the study.
Clinical Sites:	Mount Sinai Hospital, New York, NY
Time Course:	Expected duration of patient enrollment is approximately 2 years.
Subject Description:	Subjects will only be eligible for this study if they are \geq 16 years of age and have a history or suspected history of ventricular arrhythmias.
Primary Endpoints:	
 1. Freedom from recurrent ventricular arrhythmias at 6 months 2. Procedural complications (death, stroke, myocardial infarction, heart failure, conduction abnormalities, pericardial effusion requiring drainage, hematoma, pseudoaneurysm)
Secondary Endpoints:	
 1. Post-ablation inducibility 2. Time to termination 3. Total duration of intramural needle ablation 4. All-cause mortality
	(For patients who have been re-enrolled after the six-month follow-up is complete, primary and secondary endpoints will be re-assessed at six months post-second procedure.)
Primary Analytical Analysis:	N/A
Secondary Analytical Analysis:	N/A
Study Sponsor:	[name]. Icahn School of Medicine at Mount Sinai [name]

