6 ENDPOINTS

6.1 Primary Endpoint

1. Freedom from recurrent ventricular arrhythmias at 6 months, defined as sustained ventricular tachycardia lasting longer than 30 seconds or a decrease in ventricular arrhythmias (defined as unifocal PVCs, couplets, non-sustained VT) to less than 5000 ventricular beats per 24 hours and identified due to clinical symptoms, device interrogation, or 24-hour ambulatory monitoring.
2. Procedural complications (death, stroke, myocardial infarction, heart failure, conduction abnormalities, pericardial effusion requiring drainage, hematoma, pseudoaneurysm)

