10 STUDY PROCEDURES

10.1. PRE-PROCEDURE EVALUATION

Patients will be consented for the study in either the inpatient or outpatient setting. The consent will detail the use of RF energy as part of standard of care in all patients undergoing VT ablation, and INA ablation as an experimental procedure employed only if patient had an unsuccessful ablation within six months prior to enrollment or if the index ablation procedure proves unsuccessful. Unsuccessful ablation is defined as the inability to terminate ventricular arrhythmias or ventricular arrhythmias that are still inducible following ablation.

The following tests and procedures will occur before the ablation as a routine part of pre-procedural medical assessment (all done within 30 days prior to procedure unless noted below):

- Recording of patient medical history (including details of VT both clinical/ICD)
- Recording medication history (including all anti-arrhythmic drugs used and duration of use)
- Obtain β-HCG in females of child bearing age the morning of the procedure as per usual clinical practice
- Baseline assessment of arrhythmia burden and type:
 - Office/inpatient records, ICD interrogation report

- For patients being considered for PVC ablation only: 24-Hour Holter monitoring (within three months)
- Review pre-procedural imaging (within three months): MRI/CT (optional), TTE.
- Baseline laboratory, including complete blood count, standard electrolyte panel, renal function, and brain natriuretic peptide levels.
- Consent must be obtained before the VT ablation procedure.

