10.4 POST-PROCEDURE

10.4.1 POST-PROCEDURE FOLLOW UP

- All patients will be monitored to verify vascular hemostasis prior to discharge from the hospital.
- The majority of patients will receive either warfarin or a novel oral anti-coagulant (dabigatran, rivaroxaban, or apixaban) for 4-6 weeks post-procedure. Those patients with less extensive ablations may receive oral aspirin (81-325 mg daily) or clopidogrel (75 mg daily). These decisions will be made at the discretion of the primary operator per current guidelines.
- A proton pump inhibitor is recommended for any significant esophageal temperature rises noted during the procedure as determined by the treating physician. However, if the esophageal temperature is noted to have been $\geq 41.0^{\circ}\text{C}$, a proton pump inhibitor is required for a minimum of 4 weeks following the ablation procedure.
- Medication and adverse event review will be performed prior to discharge.
- Complications including vascular, stroke, heart failure, pericardial effusion, tamponade, bleeding, and death will be documented.
- The total number of episodes of VT, ATP, and shocks will be documented at all visits.

- The follow-up includes:
 - 2 weeks: Telephone follow up
 - Assessment for adverse events or recurrent arrhythmia.
 - 6 months: In-office follow up
 - History and Physical
 - Electrocardiogram
 - ICD interrogation (may be trans-telephonic)
 - Review of medications and adverse events
 - For PVC ablation patients only: 24-Hour Holter monitoring

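### VT patients need no minimum number or recency of spontaneous episodes, so the 6-month freedom percentage can include successes that owe nothing to the needle, and Section 17 plans no baseline comparison to show how many

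*Combined protocol and SAP*

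**What the plan says.** **Entry.** Criterion 1a in Section 7.1 asks for "a) monomorphic ventricular tachycardia (VT"), with no number of episodes and no period in which they must have occurred. The PVC route in 1b is quantified: "frequent ventricular arrhythmia (defined as unifocal PVCs, couplets, non-sustained VT) with a PVC burden" of at least 13%, or an LVEF decline to 40% or below. Criterion 4 requires "Clinical indication for catheter ablation of VT" but no frequency. Criterion 5 requires an arrhythmia that standard ablation could not terminate, "or previous failed ablation within 6 months prior to enrollment". Section 10.1 defines an unsuccessful ablation by non-termination or continued inducibility. Section 9 makes patients who are not inducible and not ablated screen failures. The Subject Description in the Protocol Summary speaks of subjects who "have a history or suspected history of ventricular arrhythmias".

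**Endpoint.** Section 6.1 gives freedom from recurrent ventricular arrhythmia at 6 months, "defined as sustained ventricular tachycardia lasting longer than 30 seconds" or, for ectopy, a fall below 5000 ventricular beats per 24 hours. Taken literally the first half defines freedom as having VT; the evident meaning is no sustained VT. Section 10.4.3 adds that a repeat needle ablation within 6 months is a treatment failure.

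**Data and analysis.** Baseline work includes "Recording of patient medical history (including details of VT both clinical/ICD") and an ICD interrogation (Sections 5 and 10.1). After the procedure, "The total number of episodes of VT, ATP, and shocks will be documented at all visits" (Section 10.4.1). Section 17 reports the co-primary endpoints as percentages of the study population. It names no comparator, benchmark or before-after analysis.

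**The concern.** The VT success criterion looks only forward. A patient whose untreated episodes are usually more than 6 months apart is likely to pass it whatever the needle does. None of the entry conditions excludes such a patient: the clinical indication sets no rate, the failed-ablation rule dates a procedure rather than an episode, and inducibility in the laboratory is not a measure of how often VT occurs spontaneously.

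A randomised control would show this background freedom. Here there is none, and the plan does not put the baseline VT rate beside the result. What is at stake is how the 6-month freedom percentage can be read, since a given figure could reflect ablation, infrequent VT, or a quiet spell after a cluster of episodes. For the success percentage, the error runs in one direction, in favour of the device.

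**Working it through.** **The plan's own figure.** Section 8 has no power calculation. Its one derived number is the evaluable sample: 200 × (1 − 0.66) = 68, given as approximately 70. It reproduces.

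**Inputs that must be assumed.** The documents give no VT rate. All rates, shapes and the 24-month window below are assumptions. The 6-month horizon is from Section 6.1.

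**Step 1: one patient, no treatment effect.** For r episodes per year, the Poisson chance of none in 6 months is exp(−0.5r). With clustering (negative binomial, k = 1) it is 1/(1 + 0.5r).

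| Episodes per year | Poisson | Clustered, k = 1 |
|---|---|---|
| 0.5 | 78% | 80% |
| 1 | 61% | 67% |
| 2 | 37% | 50% |
| 4 | 14% | 33% |
| 12 | 0.2% | 14% |

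**Step 2: a cohort.** Let each patient's rate per 6 months follow a gamma distribution with mean m and shape k, with Poisson counts given the rate. The chance of no episode in t half-years is P0(t) = (k/(k + mt))^k. With no treatment effect:

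- A, freedom if entry needs at least one episode in the past 24 months: [P0(1) − P0(5)] / [1 − P0(4)].
- B, freedom if entry needs at least one in the past 6 months: [P0(1) − P0(2)] / [1 − P0(1)].
- A − B is the part due to having no recency rule.

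Example, m = 2, k = 1: P0(1) = 0.3333, P0(2) = 0.2000, P0(4) = 0.1111, P0(5) = 0.0909. A = 0.2424/0.8889 = 27.3%. B = 0.1333/0.6667 = 20.0%. A − B = 7.3 points.

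| m | k | A | B | A − B (points) |
|---|---|---|---|---|
| 1 | 0.5 | 41.4% | 30.8% | 10.6 |
| 1 | 1 | 41.7% | 33.3% | 8.3 |
| 1 | 2 | 40.8% | 35.0% | 5.8 |
| 2 | 0.5 | 30.2% | 20.6% | 9.6 |
| 2 | 1 | 27.3% | 20.0% | 7.3 |
| 2 | 2 | 23.1% | 18.5% | 4.6 |
| 5 | 0.5 | 19.1% | 11.9% | 7.2 |
| 5 | 1 | 13.5% | 9.1% | 4.4 |
| 5 | 2 | 7.7% | 5.9% | 1.8 |

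Differences are taken before rounding. The attributable part runs from 1.8 to 10.6 points and is below 5 in three of nine scenarios. If all 70 evaluable patients were VT patients, that is 70 × 0.018 = 1.3 to 70 × 0.106 = 7.4 patients.

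**Step 3: patients with a quiet pre-window.** In the same model, the share of entrants with no episode in the prior 6 months is [P0(1) − P0(4)] / [1 − P0(4)], which ranges from 7% to about 37%. The share of these who stay free with no effect is [P0(2) − P0(5)] / [P0(1) − P0(4)], from 30% to 60%.

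**Reading.** Column B is still 6% to 35%. A recency rule, or a denominator restricted to recent VT, would leave most of the no-effect freedom in place.

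**The case against.** The study is observational, with a sample size set by feasibility and no hypothesis test, so no error rate is inflated. That stands: the harm is to interpretation only.

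The entry gates together narrow the population well beyond any monomorphic VT. A patient needs a clinical indication and a failed or failing standard ablation, and is dropped if not inducible and not ablated. If those treated mostly have frequent VT, the bias is small; at 12 episodes a year chance freedom is 0.2% (Poisson). This also stands, but no criterion requires frequent VT, and the planned report would not show whether it was so.

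A reader might infer that the whole no-effect freedom of 8% to 42% (column A) comes from the loose entry rule. It does not: most of it remains after requiring a recent episode, and it belongs to the single-arm design. A reader might also infer that efficacy rests on this percentage alone. Section 6.2 lists post-ablation inducibility and time to termination, acute measures that do not depend on spontaneous VT frequency. Nor does the Protocol Summary's mention of a suspected history loosen the operative criteria in Section 7.1.

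Finally, Section 17 says baseline characteristics will be analysed and gives examples only, so reporting baseline VT is not ruled out. It is not specified either.

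**Conclusion.** The point holds as a gap in interpretation. VT patients can enter with no minimum number or recency of spontaneous episodes, VT success is an absolute 6-month state (no sustained VT, no repeat needle ablation), and the percentage is reported without control or baseline. Patients with infrequent VT can be counted as successes without a treatment effect. The documents do not support saying that they will be, or how many, because they give no VT rates and no split between VT and PVC patients.

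The part due to the missing recency rule is about 2 to 11 points under assumed gamma-Poisson rates (mean 1, 2 or 5 episodes per 6 months, shape 0.5 to 2). The 24-month look-back stands in for an unlimited one; a longer window would raise the figure and a shorter one lower it. The issue concerns VT patients; those entering on PVC burden have a baseline threshold. It is a cheap and worthwhile improvement to the analysis, and does not call for a new denominator or new eligibility rules.

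**What to change.** Keep the primary endpoint denominator as planned. Add to Section 17, for VT patients:

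1. **Baseline counts.** The number of sustained VT episodes in the 6 months before the procedure, and separately the numbers of ATP and shock therapies, from the baseline ICD interrogation and clinical records.
2. **Freedom by baseline group.** Six-month freedom shown separately for patients with and without at least one sustained VT episode in that window, with a statement that freedom in the second group is not by itself evidence of efficacy.
3. **Within-patient comparison.** Counts for the 6 months before against the 6 months after, with the same event definition on both sides. Sustained VT over 30 seconds should be compared with itself, and ATP and shocks each with themselves, so that a patient does not qualify on one kind of event and succeed on another. Report antiarrhythmic drug use alongside, since Section 10.4.2 leaves it to the investigator, and flag any failed standard ablation inside the pre-window, which criterion 5 allows.

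**Cost.** One case report form field with a fixed 6-month look-back, which Sections 5 and 10.1 do not now define, and the wording above. Counts will be less complete in patients without an ICD. The result may read less favourably. Some regression to the mean will remain in the before-after comparison and should be acknowledged when it is reported.

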7.2 EXCLUSION CRITERIA

1. History of MI or CABG within 6 weeks.
2. NYHA Class IV CHF.
3. Patients with idiopathic ventricular arrhythmias defined as VT or PVCs that occur without evidence of structural heart disease and that are not causing significant depression of LV function.
4. Women known to be pregnant or to have positive beta-HCG.

5. Definite protruding left ventricular thrombus on pre-ablation echocardiography or other imaging modalities.
6. Contraindication to heparin
7. Allergy to radiographic contrast dye.
8. Unstable angina that is not due to frequent or incessant VT.
9. Acute non-cardiovascular illness or systemic infection.
10. Thrombocytopenia (platelet count < 50,000 mm³) or coagulopathy.
11. Cardiogenic shock unless it is due to incessant VT.
12. Unable to sign consent.
13. Projected lifespan of < 1 year.

8 SAMPLE SIZE

This safety and efficacy study will enroll up to 200 patients across 1 US center. This number has been determined on the basis of study feasibility and not by statistical means. In a similar trial, we have experienced a 66% screen failure rate; as such, with 200 patients enrolled, we expect to have approximately 70 evaluable patients who have undergone the INA procedure.

[figure not shown]
9 PATIENT ENROLLMENT AND WITHDRAWAL

Patients meeting the study inclusion criteria will be identified in the outpatient or inpatient setting by one of the study sites' primary or co-investigators. Patients will be followed by one of the study site primary or co-investigators. Approximately 100 patients are expected to participate each year, with an expected total enrollment of 200 patients.

The study will typically be described (including the risks and benefits) during the initial clinic or hospital visit. Consent will typically be obtained at the time of the initial assessment if it is clear that the patient truly understands the nature of the study. Alternatively, the patient will be encouraged to take a copy of the consent form home to contemplate whether he/she would like to be enrolled in the study (see Appendix 1 for informed consent form.) Only patients who voluntarily provide consent will be included in this study. Consent will be obtained prior to undergoing the ablation procedure. Patients will be able to withdraw from the study at any point without compromising their medical care. All data will be de-identified and protected in accordance with institutional and HIPAA guidelines, including 1) de-identification of all geographic subdivisions smaller than a state; 2) all elements of dates related to the individual; 3) telephone and fax numbers; 4) email addresses; 5) social security, medical record, health plan beneficiary, account, and certificate/license numbers; 6) vehicle identifiers; 7) device identifiers; 8) URLs and IP addresses; 9) biometric identifiers; and 10) photographic images.

For potential patients aged < 18, parental consent will be required along with subject assent.

Eligible subjects will be consented for participation in the trial prior to undergoing VT ablation. Patients are considered enrolled once consented. Patients whose VT is not inducible and no VT ablation is performed during the procedure will be considered to be screen failures. No follow-up will be performed with subjects who have no VT ablation during the procedure. Patients successfully treated with standard ablation once enrolled will be enrolled and will be followed in a registry for 6 months (adhering to the same post-procedure schedule as the patients that underwent INA).

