5 SCHEDULE OF TREATMENT AND TESTS

TABLE 1: SCHEDULE OF TREATMENTS AND TESTS:

	Baseline (within 30 days)	Procedure	Discharge	Telephone Follow-up (2 weeks +/- 3 days)	Follow-up Visit (6mo, +/- 2 weeks)
Type of visit	Office	Hospital		N/A	Office
Informed Consent	X				
Brief History & Physical	X				X
Blood Laboratory Testing: CBC, Electrolytes, BUN/Creatinine, BNP, INR, LFTs	X				X (as indicated)
TTE	X (within 3 months)				
CT/MRI (optional)	X (within 3 months, if done)				
*24-Hour Ambulatory Monitor	X (within 3 months)				X
ICD Interrogation	X				X
Ablation Procedure		X			
EKG	X				X
Medications	X	X	X	X	X
Adverse Events		X	X	X	X

*24-hour ambulatory monitoring will only be required for those undergoing ablation for frequent ventricular arrhythmia (defined as unifocal PVCs, couplets, non-sustained VT) that is causing a decline in LV ejection fraction to $\leq 40\%$.

Patients whose VT is successfully treated with standard ablation once enrolled will be placed in a registry and will continue to be followed throughout the study, adhering to the same post-procedure schedule as the patients who underwent intramural needle ablation. Patients whose VT is not inducible and no VT ablation is performed during the procedure will also be considered screen failures. No follow-up will be performed with subjects who have no VT ablation during the procedure.

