10.3 VT ABLATION PROCEDURAL DETAILS

- Patients will be brought to the electrophysiology laboratory in a fasting state.
- General anesthesia or conscious sedation will be used for sedation.
- Patients will undergo electrophysiology study and VT ablation as per standard practice.
- If a patient's arrhythmia cannot be eliminated with standard ablation or if the patient has failed ablation by standard technique, the patient will undergo INA. The INA hardware/software will be employed as described above.
- Therapeutic anticoagulation will be administered with intravenous heparin with a target ACT of 300 seconds or greater.
- Esophageal temperature monitoring is required when ablation is performed in the coronary sinus or epicardium irrespective of whether standard ablation or intramural needle ablation is performed. Ablation should be stopped when esophageal temperature is $\geq 38.5^{\circ}\text{C}$.
- Procedural endpoint will be non-inducibility of clinical VT.

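### Patients who qualify for needle ablation but do not receive it have no assigned cohort or follow-up, and the plan does not settle how they count for efficacy

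*Combined protocol and SAP*

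**What the plan says.** Patients count as enrolled at consent, before the procedure (Section 9). The text then gives them three destinations.

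- **Screen failure.** The Protocol Summary puts here anyone not ablated within 90 days of enrolling. Sections 5 and 9 add patients whose VT cannot be induced and who have no ablation. Section 9 states: "No follow-up will be performed with subjects who have no VT ablation during the procedure".
- **Registry.** Section 5: "Patients whose VT is successfully treated with standard ablation once enrolled will be placed in a registry". Section 9 says the same: "Patients successfully treated with standard ablation once enrolled will be enrolled and will be followed in a registry for 6 months". These patients keep the post-procedure schedule used for INA patients.
- **Evaluable.** Section 8: "we expect to have approximately 70 evaluable patients who have undergone the INA procedure".

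Section 10.3 covers patients whose arrhythmia standard ablation cannot eliminate, and patients with an earlier failed standard ablation. For both it says that "the patient will undergo INA". It makes no provision for INA that is planned or started but not delivered.

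Section 17 reports both co-primary endpoints as percentages of a total study population that it does not define.

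**The concern.** The objective in Section 2 concerns patients in whom standard RF ablation has failed. Some of them may need the needle and not get it: the catheter may not reach the target, the needle may not deploy, the patient may become unstable, or the operator may stop. The protocol itself makes this foreseeable, because Section 4.1 requires contrast staining to be confirmed under fluoroscopy before power is applied, and that check can fail.

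These are technical failures of the needle approach. If they sit outside the analysed group, the 6-month freedom rate can look better than it would among all patients for whom the needle was intended. If nobody is told to follow them, their outcomes cannot be recovered at analysis. The study is single-arm and reports only percentages, so the denominator carries much of the result.

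**Working it through.** **1. The plan's own figure.** Section 8 gives 200 enrolled and a 66% screen failure rate: 200 × (1 − 0.66) = 68, against the stated figure of approximately 70. It reproduces to within 2 patients. This arithmetic divides all 200 into screen failures and INA-treated patients. It leaves no share for the registry or for non-delivery. Either the 66% covers more than the screen failures that the text defines, or the 70 is too high.

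**2. Where each course leads.**

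| Course after consent | Cohort | Follow-up |
|---|---|---|
| VT not inducible, no ablation | Screen failure | None (Sections 5, 9) |
| Standard ablation succeeds | Registry | 2 weeks and 6 months |
| Needle RF delivered | Evaluable (Section 8) | 2 weeks and 6 months |
| Standard ablation delivered and fails, no needle RF | None named | Unassigned |
| Prior failed ablation, straight to the needle, none delivered | None named at the procedure; a screen failure under the Protocol Summary only if no ablation follows within 90 days | Ended by the literal Section 9 wording, since no ablation took place |

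The last two rows are the gap.

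**3. The two readings of the denominator.**

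- Evaluable patients who underwent INA (Section 8): the last two rows drop out.
- All consented patients (one reading of Section 17): they are included, but so are screen failures and registry patients. For example, 35 successes, which is 50% of 70, would read 35/200 = 17.5%. That does not measure INA.

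Neither gives the freedom rate among patients for whom the needle was intended.

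**4. Size.** Let p be freedom in the treated set, f the fraction of INA-intended patients who receive no needle RF, and g the freedom rate in that fraction.

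Freedom in the intended set = (1 − f) × p + f × g. The difference from p is f × (p − g), which is largest at g = 0. Counting every non-delivery as a failure therefore gives p × (1 − f), an upper bound on the bias for a given f. The intended set has 70/(1 − f) patients.

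The documents give neither f nor p; the values below are assumptions.

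| f | Intended set | Patients added | p = 50% becomes | p = 60% becomes |
|---|---|---|---|---|
| 3% | 70/0.97 = 72.2 | 2.2 | 48.5% | 58.2% |
| 10% | 70/0.90 = 77.8 | 7.8 | 45.0% | 54.0% |
| 15% | 70/0.85 = 82.4 | 12.4 | 42.5% | 51.0% |

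**The case against.** A reader might infer that these patients get no follow-up and leave the efficacy denominator. The documents do not support either as a general statement.

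- **Follow-up.** The no-follow-up rule reaches only subjects with no ablation, so it does not apply where standard ablation was delivered and failed. Section 10.4.1 lists the 2-week and 6-month contacts without restricting them to a cohort, and Table 1 has no such restriction either. An enrolled, ablated patient could reasonably be followed under these. This stands: for that group, follow-up is unassigned, not withdrawn. Only the patient who went straight to the needle is caught by the literal rule.
- **Denominator.** The evaluable group in Section 8 belongs to a recruitment forecast and is not a defined analysis set, while Section 17 governs the analysis. If its total study population means everyone consented, the patients are in. This also stands, but that reading does not yield an INA success rate.
- **Meaning of having undergone INA.** The plan does not say that RF must have been delivered. A procedure started and abandoned might be counted. That is possible, and the text does not settle it.
- **Size.** Section 10.3 makes INA the expected next step, so the group may be small. At f = 3% the shift is 1.5 points. Some undelivered patients might also be free of arrhythmia at 6 months.
- **Objective.** An as-treated result is a defensible target for a single-arm device study. It remains in the proposal, with the intended set shown beside it.
- **Missing figure.** A figure in Section 8 is not visible in the copy reviewed and could place these patients. The text of Sections 5, 8, 9 and 10.3 does not.

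**Conclusion.** The point holds as a gap in cohort, follow-up and denominator. A patient who meets the Section 10.3 condition for INA but receives no needle RF has no assigned cohort. Follow-up is unassigned if standard ablation was delivered and failed, and ended by the wording of Section 9 if a prior-failure patient went straight to the needle and none was delivered. The plan does not say that all such patients are lost to follow-up or removed from the analysis, and the point should not be put that way.

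The efficacy denominator is either the INA-treated patients, which can bias freedom upward, or an undefined population which, if read as all consented patients, does not measure INA.

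The size cannot be fixed from the documents. The move from 50% to between 48.5% and 42.5% rests on an assumed f of 3% to 15%, an assumed 50% freedom among the treated, and every non-delivery counted as a failure. The change is still worth making, because follow-up that was not done cannot be supplied at the analysis stage.

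**What to change.** 1. In Sections 5, 9 and 17, define an INA-intended set: every patient who meets the Section 10.3 condition at the index procedure, whether or not needle RF was delivered. This covers patients whose standard ablation failed at that procedure, and patients with a prior failed ablation in whom INA was planned or started.
2. Assign this set the existing 2-week and 6-month contacts, and word the no-follow-up rule in Sections 5 and 9 so that it does not reach these patients.
3. Report the delivery rate, INA delivered / INA intended.
4. Report 6-month freedom in the INA-intended set, with non-delivery counted as failure, and complications in the same set, each beside the INA-treated result. Section 10.4.3 already counts a repeat INA within six months as a treatment failure, so a rule of this kind fits the plan.
5. Replace the total study population in Section 17 with these named sets.

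The cost is protocol wording, one telephone call and one visit for what may be a few patients, and a slightly less favourable freedom rate. Treatment does not change.
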